#### 6.1.6. Handheld Dynamometry

The HHD will be derived as follows:

- For each muscle, calculate the percent of Baseline:  $100 \times (Post-baseline raw value/Baseline raw value)$ . If both the post-baseline and baseline values are 0, then the ratio=100. If the post-baseline value is greater than 0 but the baseline was zero, then the ratio is set to missing.
- Three Megascores will be summarized based on muscle location (upper limbs, lower limbs and total). The score for each will be derived as the average of the non-missing ratio for the muscles used in the calculation.
- Megascore is set to 100 at Baseline when HHD assessment is available.

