## 4.4. Exploratory Endpoints

All exploratory endpoints will be analyzed using the Randomized Set. These analyses will be descriptive in nature. For these endpoints, if any participant experiences a relevant IE of acute therapy with standard DM treatment/prohibited medication or treatment discontinuation due to AE, lack of efficacy, or death, the data will be set to missing after the IE and there will be no imputation.

#### 4.4.1. Change From Baseline in EQ-5D-5L at Week 26

The European Quality of Life Health 5-item questionnaire dimensions 5-level (EQ-5D-5L) is self-assessed instrument. This instrument consists of 5 domains (mobility, self-care, usual activities, pain/discomfort, and anxiety/depression) and VAS. The VAS ranges from 0 to 100, where lower values represent the worst QoL.

Descriptive statistics of actual and change from Baseline in VAS will be presented by treatment and scheduled visit. For each of the 5 domains, categorical summaries of the percentage of participants reporting ordinal responses (1 to 5) will be presented by treatment and scheduled visit. In addition, an overall shift table of Baseline to worst post-Baseline during the RCP will be generated by treatment arm for each of the 5 domains.

## 4.4.2. Change From Baseline in PROMIS-29 v2.1 Domains at Week 26

The Patient-Reported Outcomes Measurement Instrument System (PROMIS)-29 v2.1 is a QoL instrument used to assess pain intensity on a Likert scale for each of the health domains (physical function, fatigue, pain interference, depressive symptoms, anxiety, ability to participate in social roles and activities, and sleep disturbance) using 4 items per domain. For each of the health domains, a total score will only be calculated if there are no missing items per domain. The total score will be the sum of the responses for each question.

Descriptive statistics of actual and change in total score will be presented by treatment arm and scheduled visit.

## 4.4.3. Change From Baseline in Short Form Health Survey (36 Questions Version) at Week 26

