## 4.4.8. Incidence of Protocol-Defined CW During RCP

A time-at-risk-adjusted incidence rate will be calculated. This incidence rate is defined as the number of participants who experience CW divided by the total person-years at risk for the event. CW during the RCP will be defined as a participant meeting the criteria as specified in Section 4.3.10 at 2 consecutive visits. The total person-years at risk will be defined differently for participants with and without the event of CW. For participants with an event, the risk is defined as (date of the criteria being met for CW - first dose date + 1)/365.25. If the participant did not experience an event, the risk is defined as (latest visit date of TIS during the RCP - first dose date + 1)/365.25. Total person-years at risk will be the sum of the person-years at risk for all participants in each treatment group. A summary table displaying the total person-years at risk and the number of participants with an event will be displayed.

## 4.4.9. Change From Baseline in Handheld Dynamometry Performance at Week 26

Handheld dynamometry is a procedure for quantitative strength testing. Muscle strength testing will be performed at baseline and Week 26. Derivations are specified in Section 6.1.6.

Descriptive statistics of actual values and change from Baseline will be summarized by visit for the handheld dynamometry (HHD) data.

#### 4.4.10. Change From Baseline in 30-second Chair Stand Test (30s CST) at Week 26

The 30-second Chair Stand Test (30s CST) will count the number of times the participant is able to stand in 30 seconds at baseline and Week 26. Descriptive statistics will be generated.

#### 4.4.11. Change From Baseline in Functional Assessment of Chronic Illness Therapy – Fatigue Scale at Week 26

Descriptive statistics of actual and change from Baseline in Functional Assessment of Chronic Illness Therapy – Fatigue Scale (FACIT-Fatigue) scores at each visit will be generated.

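### The handheld-dynamometry Megascore drops a muscle that recovers from zero but counts one that falls to zero, so regained force is never credited and regaining it can lower the score

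*SAP*

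**What the plan says.** SAP 6.1.6 derives three Megascores: upper limbs, lower limbs and total. The starting point is "For each muscle, calculate the percent of Baseline", that is, 100 × follow-up force / baseline force. Two exceptions follow:

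- A muscle reading zero on both occasions is assigned 100.
- For a muscle that starts at zero and regains force, the rule is: "If the post-baseline value is greater than 0 but the baseline was zero, then the ratio is set to missing".

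Nothing is written for a positive baseline with a follow-up reading of 0. The formula then gives 0, and that value stays in. Each Megascore is "derived as the average of the non-missing ratio for the muscles used in the calculation". The reference point is fixed: "Megascore is set to 100 at Baseline when HHD assessment is available".

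SAP 4.4.9 sets the reporting, with measurements at baseline and Week 26: "Descriptive statistics of actual values and change from Baseline will be summarized by visit for the handheld dynamometry (HHD) data". Of all the exploratory endpoints, SAP 4.4 says: "These analyses will be descriptive in nature".

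Protocol 8.1.11 describes bilateral testing of prespecified upper- and lower-limb muscles. Neither document gives the number of muscles, the measurement error or the frequency of zero readings.

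**The concern.** Two features of the derivation bear on the reported change.

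The first is the zero rule. A gain from zero and a loss to zero are mirror images, yet the gain leaves the calculation and the loss enters at the lowest possible value. Whether a zero-baseline muscle is kept depends on its follow-up reading, so the set of muscles averaged is chosen by the post-randomisation outcome. An effective treatment would lose more muscles from its own arm.

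The second is the mean of ratios. Random error in a denominator raises the expected ratio, so the score can move above 100 when nothing has changed.

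Because the Megascore is 100 at Baseline by definition, both features pass directly into change from Baseline. Within-arm change matters most in the open-label extension, where Protocol Table 9 lists dynamometry as an endpoint and there is no concurrent placebo group.

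**Working it through.** The plan states no dynamometry effect, SD or zero frequency, so there is no figure to reproduce. The rules of SAP 6.1.6 are applied literally. Muscle counts, force values, CVs and the detection floor are assumptions.

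**1. Zero rule, worked cases (no assumption about frequency)**

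- Six muscles, baseline 0, 0, 10, 10, 12, 12 and follow-up 3, 4, 10, 10, 12, 12. The first two are dropped and the other four ratios are 100, so the Megascore is 100. Total force rose from 44 to 51, and 100 × 51/44 = 115.9.
- The same readings reversed: (0 + 0 + 4 × 100)/6 = 66.7. By total force, 100 × 44/51 = 86.3.
- Ten muscles, eight unchanged at 10, one going 0 to 5 and one going 5 to 0. The Megascore is (8 × 100 + 0)/9 = 88.9. Total force is 85 at both visits, a ratio of 100.
- Ten muscles, nine at 90% of baseline and the tenth at baseline 0. If it stays at 0, (9 × 90 + 100)/10 = 91. If it recovers to any force, it is dropped and the score is 90.
- The same case with the nine at 110%: 109 if the tenth stays at 0, 110 if it recovers. Dropping the muscle moves the score to the mean of the others, whatever force was regained.

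**2. Zero rule, by frequency**

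Suppose a share q of muscles falls to 0, a share q rises from 0 and the rest are unchanged. The Megascore is 100(1 − 2q)/(1 − q). For q = 1%, 2%, 5% and 10% this gives 99.0, 98.0, 94.7 and 88.9.

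**3. Mean of ratios, no zeros and no true change**

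With independent log-normal error of coefficient CV at each visit, the expected ratio is 100(1 + CV²). At CV 10%, 20% and 30% this gives 101, 104 and 109. With 12 muscles and the same CV range, a ratio of sums averages 100.1 to 100.8.

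In a simulation of 24 and 12 participants, each arm drifts by this amount, but the mean between-arm difference is −0.06 to 0.05 when treatments do not differ. With a true 10% gain, the difference is 10.1 to 10.9.

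**4. Both features together**

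The simulation uses ten muscles. True strength is normal with SD 4 (3 in the last row), error SD is 1.5, and readings below 2 are recorded as 0. Units are arbitrary. The ratio of means is 100 × mean follow-up / mean baseline, pooled over all muscles. Dropped means baseline 0 and follow-up above 0.

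| Mean strength | No change: dropped | Megascore | Ratio of means | Gain of 1.5: dropped | Megascore | Ratio of means |
|---|---|---|---|---|---|---|
| 15 | 0.1% | 101.3 | 100.0 | 0.1% | 112.4 | 110.0 |
| 10 | 1.3% | 101.9 | 100.0 | 2.1% | 119.6 | 115.0 |
| 8 | 2.9% | 101.0 | 100.0 | 4.8% | 122.4 | 118.7 |
| 6 | 5.1% | 99.1 | 100.0 | 9.0% | 123.4 | 123.9 |
| 4 | 8.5% | 95.7 | 100.0 | 15.2% | 124.8 | 135.9 |

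Under no change the Megascore runs from 95.7 to 101.9, on both sides of 100. In the last row a real gain nearly doubles the share dropped, from 8.5% to 15.2%. The contrast between gain and no change there is 124.8 − 95.7 = 29.1 by Megascore and 135.9 − 100.0 = 35.9 by ratio of means. The two scores weight muscles differently, so their gap is not all error. In the first three rows the Megascore contrast is the larger one.

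**The case against.** The strongest reply is that this is a small matter on an endpoint nothing depends on. Dynamometry is exploratory and summarised descriptively. Strength is also analysed through MMT-8, a secondary endpoint (SAP 4.3.3) scored 0 to 150 without ratios, so recovery from zero is captured there. Zero readings may also be rare. Protocol 5.1 admits MMT-8 scores up to 142 of 150. Protocol 5.2 excludes significant muscle damage at the investigator's discretion, and conditions that prevent quantitative strength testing. At 1 to 2% of muscles in each direction, the zero rule costs only 1 to 2 points. All of this stands and limits the importance of the point. It does not make the rule right, because the worked cases need no assumption about frequency.

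A second reply is that a ratio of sums is not plainly better. It favours strong muscles: with baselines of 5 and 40, doubling the weaker one gives 100 × 50/45 = 111, against (200 + 100)/2 = 150 for the mean of ratios. It is undefined when every baseline in a limb score is 0. This also stands, and it argues for showing both scores rather than replacing one.

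A reader might infer that the Megascore is biased upward overall. The documents do not support that. The upward drift needs measurement error they do not quantify, and the zero rule pulls the other way. A reader might also infer that the placebo comparison is biased under no effect. It is not: both arms then carry the same distortion, and the simulated difference is about 0.

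**Conclusion.** The zero rule in SAP 6.1.6 gives a wrong result as written. Force regained from zero earns no credit, the mirror-image loss is charged in full, and recovery can lower the score (91 to 90). It does not always lower it; the direction depends on whether the other muscles average below or above 100. Because exclusion depends on the follow-up reading, within-arm change is distorted. A real effect can be understated if zero baselines are common, about 29 against 36 points in the weakest assumed setting.

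The mean-of-ratios drift, 1 to 9 points at assumed CVs of 10 to 30%, is a separate and opposing effect that largely cancels between arms when there is no treatment difference. The net sign of the within-arm distortion cannot be settled from the documents.

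This is a minor point: worth correcting because the correction is cheap, with no bearing on any test or decision in Part A.

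**What to change.** In SAP 6.1.6:

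- Add, for each of the three limb groupings, 100 × (sum of follow-up force / sum of baseline force) over muscles measured at both visits. Recoveries from zero then stay in.
- State that this score is missing only when all baseline values in that grouping are 0.
- Keep the equal-weight Megascore and report it alongside.
- Tabulate by arm the number of muscles dropped from the Megascore because of a zero baseline.

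The cost is a few sentences in the SAP, one programming line for the added score and one small table. No new data are needed. The downside is that a ratio of sums gives stronger muscles more weight, which is why both scores should be shown.

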## 6.2. Study and Participant Characteristics

#### 6.2.1. Participant Disposition

A summary of participants who did not satisfy the inclusion/exclusion criteria will be presented. A summary of the participants will be tabulated for the following categories: Screen Failure, Randomized, Treated and each of the populations sets.

In addition, the number and percentage of participants who discontinued treatment, withdrew from study, and primary reasons for either discontinuation of treatment and/or withdrawal from study will be presented. Additionally, the number of participants who completed the RCP at the Week 26 Visit will also be displayed. A participant is defined as having completed the RCP at the Week 26 Visit if the participant has an assessment at that visit. The number and percentage of participants enrolled by site will be summarized by randomized arm and overall.

Data listings of those participants who withdrew and/or discontinued treatment including the associated reasons will also be presented. A separate listing of screening failure participants with the associated reason for screen failures will be generated. In addition, a listing will be generated for any modified visits that occurred on study with the reason for the modification (eg, COVID-19, travel, and participant refusal).

## 6.2.2. Baseline Characteristics and Demographics

All summaries for baseline characteristics and demographics will be based on the Randomized Set.

Descriptive statistics of demographic characteristics, including, but not limited to, age (years), age category ( $\geq 18$  to < 65 and  $\geq 65$  years), sex, race, ethnicity, region, height, weight, and weight categories ( $\leq 30$  to < 40 kg,  $\geq 40$  to < 60 kg,  $\geq 60$  kg to < 100 kg, and  $\geq 100$  kg), and body mass index will also be presented.

Additional disease characteristics will also be summarized. The disease characteristics include baseline values for 5 of the CSMs (ie, physician global activity assessment, participant global activity assessment, extramuscular disease activity, MMT-8, and HAQ), baseline CDASI Total Activity Score, baseline CDASI damage score, and baseline CDA-IGA category.

In addition, a summary of disease characteristics will be summarized. These characteristics include summaries, but are not limited to, age of diagnosis, duration of the DM diagnosis and current/prior DM medications (as reported on DM history page) and symptoms of the DM at Screening (eg, rash, calcinosis, and fatigue) and location of the joint swelling (eg, elbow, hip, and wrist).

By-participant listings of these baseline characteristics data will be presented.

#### 6.2.3. Medical History

A complete medical history will be collected during Screening. The medical and surgical history will be coded using MedDRA (Version 25.0 or higher). Medical will be summarized for the SS by SOC, High Level Term, and PT. By-participant listings of medical history data will also be presented.

#### 6.2.4. Prior and Concomitant Medications

Prior and concomitant medications will be coded using the World Health Organization Drug Dictionary (Sep 2023 or later).

Prior medications are defined as medications that were taken prior to and stopped before the first dose of treatment (ravulizumab or placebo). Concomitant medications are defined as medications that were taken prior to and were ongoing while on study intervention or medication(s) taken on or after the first dose date of the study intervention. A tabular summary of the number and percentage of participants taking concomitant medications will be by anatomic therapeutic class (ATC) and PT. Data will be presented for the SS. A separate tabular summary of prior DM and concomitant DM medication use will be by ATC and PT.

Data listings for prior medications/concomitant medications by participant will be generated, and a separate listing for prior DM and concomitant DM medications will also be generated. There may also be additional summaries of steroid medications presented by ATC and PT.

# 6.2.5. Nonpharmacologic Therapies and Procedures, Hospitalizations, and Outpatient Medical Encounters

Separate listings will be generated for nonpharmacologic therapies and procedures, hospitalizations, and outpatient medical encounters.

## 6.2.6. **Protocol Deviations**

The number and percentage of participants with specific protocol deviations will be summarized for all enrolled participants. Protocol deviations will be presented overall as well as separately for those related to COVID-19.

## 6.3. Instrument Scoring Details

#### 6.3.1. Short Form Health Survey (36 Questions Version)

The SF-36 version 2 is a set of generic, coherent, and easily administered QoL measures. It has 36 items grouped in 8 dimensions measuring each of the following 8 health domains: physical functioning, social functioning, role limitations due to physical health, bodily pain, general health, mental health, role limitations due to emotional problems, and vitality. Eight health domains scores and 2 component scores (PCS, MCS) will be calculated. The OPTUM ProCoRE 1.5 Smart Measurement System will be used to derive the 8 domain scores and 2 component scores. The algorithms used by the software are described below (as excerpted from the User's Guide).

#### 6.3.1.1. Data Cleaning and Item Recording

First, the data are checked for out-of-range values. Out-of-range values are any values that are outside the range of acceptable item response values for the SF-36 version 2 Health Survey. Out-of-range values will be converted to missing values. Next, 10 items (BP01, BP02, GH01, GH03, GH05, VT01, VT02, SF01, MH03, MH05) are reverse scored. Reverse scoring of these items is required so that higher item response values indicate better health for all SF-36 version 2.0 Health Survey items and summary measures.

#### 6.3.1.2. Item Recalibration

For most of the SF-36 version 2 Health Survey items, research to date offers good support for the assumption of a linear relationship between the item scores and the underlying health concept defined by their scales. However, empirical work has shown that 2 items, GH01 and BP01, require recalibration to satisfy this important scaling assumptions. The bodily pain scale requires additional scoring rules because the items offer both different numbers and different content of response choices and administrations of Item BP02 depended on the response to an Item BP01 in past studies.

#### 6.3.1.3. Computation of Raw Scale Scores

After recoding and recalibrating the required item values, a raw score is computed for each scale. This score is the simple algebraic sum of the final values for all items in that scale.

#### 6.3.1.4. Transformation of Raw Scale Scores to 0 to 100 Scores

The next step involves transforming each raw scale score to a 0 to 100 scale. This transformation converts the lowest and highest possible scores to 0 and 100, respectively. Scores between these values represent the percentage of the total possible scores achieved.

#### 6.3.1.5. Transformation of Raw Scale Scores to 0 to 100 Scores

The first step in T-score based scoring consists of standardizing each SF-36 version 2 Health Survey scale using a z-score transformation. A z-score indicates how far a score deviates from the mean in standard deviation units. The z-score for each scale is computed by subtracting the mean 0 to 100 score observed in the 2009 general US population from each SF-36 version 2 Health Survey scale score (0 to 100) scale and dividing the difference by the corresponding scale standard deviation observed in the 2009 general US population. The means and standard deviations utilized are dependent on the recall period option chosen by the user, based on the SF-36 version 2 Health Survey form used to collect the data being scored.

The next step of the T-score based scoring is to linearly transform each SF-36 version 2 Health Survey z-score to have a mean score of 50 and a standard deviation of 10. This is done by multiplying each SF-36 version 2 Health Survey z-score by 10 and adding the resulting product to 50. These are referred to as "norm-based" scores. The norm-based scores will be used for the 8 domain scores.

#### 6.3.1.6. Scoring the SF-36 Version 2 Healthy Survey Component Summary Measure

The first step in scoring the component summary measures consists of standardizing each SF-36 version 2 Health Survey scale using a z-score transformation. The z-score for each scale is computed by subtracting the mean 0 to 100 score observed in the 2009 general US population from each SF-36 version 2 Health Survey scale score (0 to 100) scale and dividing the difference by the corresponding scale standard deviation observed in the 2009 general US population. The means and standard deviations utilized are dependent on the recall period option chosen by the user based on the SF-36 version 2 Health Survey form used to collect the data being scored.

After a z-score has been computed for each SF-36 version 2 Health Survey scale, the second step involves computation of aggregate scores for the physical and mental summaries using weights (factor score coefficients) derived from the 1990 general US population. These are the same weights as those used to score PCS and MCS from the SF-36 version 2 Health Survey. An aggregate physical score is computed by multiplying the z-score of each SF-36 version 2 Health Survey scale by its associated physical factor score coefficient and summing the 8 products. If any of the scale scores are missing, then the aggregate physical score is not computed. An aggregate mental score is computed by multiplying the z-score of each SF-36 version 2 Health Survey scale by its associated mental factor score coefficient and summing the 8 products. If any of the scale scores are missing, then the aggregate mental score is not computed. If any of the scale scores are missing, then the aggregate mental score is not computed. If any of the scale scores are missing, then the aggregate mental score is not computed.

The third step involves transforming the aggregate physical and mental summary scores to the T-score based (50, 10) scoring. This is done by multiplying each aggregate summary score obtained from the second step by 10 and adding the resulting product to 50.

#### 6.3.1.7. Handling of Missing Items

The maximum data recovery option will be used for missing data estimation. This results in the application of algorithms that compute a scale score for those respondents who have answered at least 1 item that represents that construct. For the physical functioning scale, item parameters obtained through item response theory methods are used to estimate a missing value on an item based on a respondent's responses to answered items. For the 7 remaining scales, a person-specific estimate based on the mean response to the answered items on the scale is used to estimate a missing value. Additionally, a PCS and MCS score is calculated for those respondents who have calculated scores on at least 7 of the 8 SF-36 version 2 Health Survey scales. However, PCS is not estimated if the physical functioning scale is missing, and MCS is not estimated if the Mental Health scale is missing.

